## J. Outcome measures

Asthma exacerbations are an outcome of interest for all participants.

For participants enrolled in the 48-week cohort study, the primary outcome is corticosteroid treatment responsiveness, assessed 14 days after systemic triamcinolone administration (at visit 2). Responsiveness will be determined from the mean difference in the Asthma Control Questionnaire (**ACQ**) score between visit 1 (baseline) and visit 2 (14 days), with a reduction of 0.5 considered a minimally important difference.

The secondary outcome for participants enrolled in the 48-week cohort study is quality of life, assessed by the PROMIS Pediatric Asthma Impact Scale (**PAIS**) at visits 3, 4 and 5. As with all PROMIS measures, the PAIS is scored on the T-score metric, with higher scores reflecting more of the concept being measured. On the T-score metric, 50 is the mean of the reference population and 10 is the standard deviation; thus scores of 40 and 60 are one standard deviation lower and higher than the mean of the reference population, respectively.

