## L. Procedural details

**Asthma control evaluation.** Asthma control and associated respiratory symptoms will also be assessed with the Asthma Control Questionnaire (**ACQ**) and the Asthma Control Test (**ACT**). The ACQ can be completed by children down to 6 years with strong measurement properties when administered by a trained interviewer. The ACQ is sensitive to short-term changes in asthma control and has well-documented reliability and cross-sectional and longitudinal validity in diverse asthma populations across a wide range of severities. This 7-item questionnaire includes questions related to daytime and nocturnal symptoms, short-acting bronchodilator use, and lung function during the clinic visit on that day. A higher score indicates poorer asthma control. The ACT can be completed directly by children 12 years and older; children 6-11 years will complete the Childhood ACT (**C-ACT**). Both tools have been extensively validated and have excellent measurement properties. For both tests, individual items about respiratory symptoms (5 and 7 in total for ACT and C-ACT, respectively) are summed; scores of 19 or less reflect uncontrolled asthma.

**PROMIS symptom questionnaires.** Symptoms will be assessed with validated PROMIS measures for children. PROMIS measures will be completed directly by children age 8-21 years, with caregiver assistance for children 6-7 years. The following PROMIS short-form measures will be utilized:

- Pediatric Life Satisfaction (4a)
- Pediatric Meaning and Purpose (4a)
- Pediatric Physical Stress Experience (4a)
- Pediatric Physical Activity (4a)
- Pediatric Positive Affect (4a)
- Pediatric Psychological Stress Experiences (4a)
- Pediatric Family Relationships (4a)
- Pediatric Asthma Impact (8a)
- Pediatric Anger (5a)
- Pediatric Anxiety (8a)
- Pediatric Depressive Symptoms (8a)
- Pediatric Fatigue (10a)
- Pediatric Peer Relationships (8a)

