## **T. Sample size**

The sample size is 173 participants age 6 up to 21 years, which accounts for a conservative attrition rate of 15% (final N=147). The following assumptions were used for sample size calculations:

- Identification of 4 symptom clusters resulting in 3 degrees of freedom,

- >80% desired power for a chi-square test of multiple proportions,
- Two-tailed significance level of 0.05 if the effect size (W) is small-to-medium by Cohen's convention and equivalent to W=0.275 (small effect: W=0.10, corresponding odds ratio=1.49; medium effect: W=0.30, corresponding odds ratio=3.45), and
- Sample size allocation ratio of 1-2 per cluster group and sample sizes of at least 20 per group.

The sample size calculations with the above parameters should achieve at least 80% power as shown in **Table 3**.

For the secondary outcome, The sample size of 173 children necessary for the primary outcome should achieve >85% power to detect a difference of 0.2 between group means (considered a small effect size  $d$ ) with standard deviation of 0.20. Power >80% is achieved if the mean difference between groups and associated standard deviation is slightly larger but still small (0.25-0.30). In our prior study of triamcinolone administration to children with asthma, mean ( $\pm$  standard deviation) quality of life scores (on a different instrument, the Asthma Quality of Life Questionnaire) were 6.17 ( $\pm$  0.75) and 5.07 ( $\pm$  0.99), respectively. If similar differences are noted between two symptom cluster groups, we should have >90% power for the primary outcome and >95% for the secondary outcome if the groups have at least 20 participants. With smaller group sizes of only 13 participants, power would be >81% and >89% for the primary and secondary outcomes, respectively.

Drop-out	df	Power if effect size is:				
		0.250	0.275	0.300	0.325	0.350
10% (N=156)	3	0.749	0.833	0.897	0.941	0.969
	4	0.703	0.795	0.867	0.920	0.956
	5	0.664	0.760	0.840	0.900	0.942
12.5% (N=151)	3	0.734	0.820	0.886	0.933	0.963
	4	0.687	0.780	0.855	0.911	0.949
	5	0.648	0.744	0.826	0.889	0.934
15% (N=147)	3	0.721	0.808	0.877	0.926	0.959
	4	0.674	0.767	0.844	0.903	0.943
	5	0.634	0.731	0.814	0.878	0.927

**Table 3.** Estimated power.

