The secondary outcome, quality of life, will be compared with generalized estimating equations at visits 3, 4 and 5 using latent class assignment as the predictor. Analyses will be evaluated in light of pertinent covariates such as age, sex, race, ethnicity, socioeconomic status, medications, exposures and allergic sensitization. A 0.05 significance threshold will be utilized for secondary analyses without adjustment for multiple comparisons.

Metabolomic data, cytokine data, and amino acid data will be quantitative, linear mixed effects models will be used to determine the association between these symptom cluster group assignment.

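### The secondary quality-of-life GEE does not name the visit-1 Asthma Impact score, so a class effect would not show prediction beyond the child's starting score

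*Combined protocol and SAP*

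**What the plan says.** - **Outcome.** Section J defines the secondary outcome as "quality of life, assessed by the PROMIS Pediatric Asthma Impact Scale" at visits 3, 4 and 5, on a T-score where "50 is the mean of the reference population and 10 is the standard deviation".
- **Model.** Section U, plan for aims 1-3, compares it with "generalized estimating equations at visits 3, 4 and 5 using latent class assignment as the predictor".
- **Covariates.** The same paragraph adds "Analyses will be evaluated in light of pertinent covariates such as age, sex, race, ethnicity, socioeconomic status", then medications, exposures and allergic sensitization. The list is illustrative, not closed. It names neither a baseline value of the outcome, nor change from baseline, nor a contrast with baseline.
- **Threshold.** "A 0.05 significance threshold will be utilized for secondary analyses without adjustment for multiple comparisons".
- **Availability of the baseline score.** Section K gives the PROMIS questionnaires at visit 1, and the section L list of those questionnaires has the item beginning "Pediatric Asthma Impact (8a".
- **How classes are made.** Section U fits the latent transition analysis (LTA) to patient-reported symptoms, ACQ, ACT, lung function, exhaled nitric oxide and eosinophils at baseline and visits 3, 4 and 5. For the primary outcome, children are assigned by the baseline posterior probability. The section does not say whether Asthma Impact is one of the indicators.
- **What is claimed.** Aim 2 in section B speaks of associations and expects the worst-symptom children to have the poorest quality of life. The overarching hypothesis in section B and the first-study list in section D say that clusters *predict* it.

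**The concern.** A class with the poorest symptoms and asthma control will probably start with a worse Asthma Impact score. Scores on such a scale tend to persist. A class difference at weeks 16 to 48 can therefore arise in two ways: class membership carries information about later quality of life that the first questionnaire does not, or children who began worse simply stay worse. The named model cannot tell these apart.

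What is at stake is the interpretation of the secondary result. If a significant class effect were reported as clusters predicting quality of life, a reader could take it to mean that clustering adds something to the Asthma Impact score already in hand. Persistence alone could produce that result. The primary outcome does not have this gap in the same form, because it uses the ACQ change from visit 1 to visit 2.

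**Working it through.** **The plan's own figures first.** Section T: 147/0.85 = 172.9, so 173 enrolled. The Table 3 entry for N=147, 3 df, W=0.275 reproduces at 0.808. For the secondary outcome, a difference of 0.2 with SD 0.20 and 20 per group gives 86.9% power (t-test), in line with the stated figure of more than 85%. These calculations reproduce, but none concerns baseline carry-over, for which the plan gives no figure.

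**Inputs for the carry-over check**
- From the documents: SD 10 (reference population, section J); N=147 and four classes, so 3 df (section T); significance level 0.05, taken as two-sided because section T says so for the primary outcome.
- Assumed, because the documents do not give them: the baseline gap; baseline-to-follow-up correlation r = 0.6; correlation 0.6 between follow-up visits; SD 10 within class; complete data; one class worse and the other three equal.
- No class effect once the baseline score is known.

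**Formulas**
- Carried-over difference: d = r × gap.
- Variance of a child's three-visit mean: v = 100 × (1 + 2 × 0.6)/3 = 73.33.
- Noncentrality of the 3-df class test: L = d² × n₁(1 − n₁/N)/v, where n₁ is the size of the worse class. For equal classes n₁ = 147/4 = 36.75, and 36.75 × 0.75 = 27.56.
- Rejection rate: the probability that a noncentral chi-square (3 df, L) exceeds 7.815.

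| Baseline gap | d | L | Unadjusted test significant |
|---|---|---|---|
| 2 | 1.2 | 1.44 × 27.56/73.33 = 0.54 | 8% |
| 5 | 3.0 | 9.00 × 27.56/73.33 = 3.38 | 31% |
| 8 | 4.8 | 23.04 × 27.56/73.33 = 8.66 | 69% |
| 10 | 6.0 | 36.00 × 27.56/73.33 = 13.53 | 89% |

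**Sensitivity**
- Classes of 21/42/42/42 with the smallest one worse: 21 × 126/147 = 18.0 replaces 27.56. Gaps of 5, 8 and 10 give 21%, 49% and 70%. If a class of 42 is the worse one, the factor is 42 × 105/147 = 30.0 and the rates are slightly above the table.
- Four classes of 20 (N=80, an assumed smaller Option 2 sample): the factor is 20 × 0.75 = 15, and a 10-point gap gives 61%.
- r = 0.3, equal classes, 10-point gap: d = 3, L = 3.38, 31%.

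**With and without the covariate.** Simulations used four equal classes with r and the between-visit correlation both 0.5, again with no class effect given baseline. The Wald test on the three-visit mean (2,000 runs) rejected in 24% unadjusted and 6% adjusted for a 5-point gap, and in 78% and 6% for a 10-point gap. A fitted GEE with exchangeable correlation (300 runs) gave 28% and 9% at 5 points, and 79% and 6% at 10 points. The small excess over 5% is mainly small-sample error of the robust variance and, in the 300-run check, simulation noise.

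These adjusted rates treat the observed baseline score as error-free. With assumed reliability of 0.9 or 0.8, a 10-point gap and a contrast of 37 children against 110, the adjusted test still rejected in about 9% or 21%.

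**The case against.** Three points on the other side stand.

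1. **The unadjusted test is valid for Aim 2.** Aim 2 asks about associations. A carried-over difference of 6 points is a true difference in later quality of life between classes, and detecting it is correct. A reader might infer that the rates above are false-positive rates for the planned test. They are not. They show how often a significant result would occur although class adds nothing to the baseline score.
2. **Baseline is unspecified, not excluded.** The text is "pertinent covariates such as age, sex, race, ethnicity, socioeconomic status, medications, exposures and allergic sensitization". A reader might infer that the plan rules out baseline adjustment, but an open list does not do that. What it does is leave the choice until after the data are seen.
3. **Adjustment has limits.** In a non-randomised comparison, conditioning on the starting score may remove part of what defines a class. It also answers a different question from Aim 2, so it should not replace the unadjusted comparison.

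What does not stand is leaving the plan as it is. Sections B and D speak of prediction, section F expects combined symptoms to give poorer outcomes than respiratory symptoms alone, and the one covariate that would separate added prediction from persistence is not named.

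**Conclusion.** The point holds as a matter of pre-specification and interpretation. The named model supports a statement that classes differ in later Asthma Impact. It does not support a statement that class predicts Asthma Impact beyond the visit-1 score.

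The size depends on inputs that the documents do not give. Under the assumptions above, carry-over alone gives a significant class test in about 8% of trials for a 2-point gap and 89% for a 10-point gap. The rates fall with a weaker correlation, a smaller Option 2 sample, or a worse class that is also the smaller one. Option 1 children have no visits 3-5, and section H refers to a subset receiving triamcinolone, so the GEE sample may be below 147.

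A reader might infer that a significant class effect is close to guaranteed. For a contrast of 37 children in the worst class against the other 110, a 10-point gap and r = 0.6, the standard error is √(73.33 × (1/37 + 1/110)) = 1.63, and a 6-point carried-over difference is significant 96% of the time. The documents do not support that as the general case: the plan assumes four classes with 3 df, names no such pooled contrast, and gives no baseline gap.

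**What to change.** In section U, pre-specify two secondary models and label each with its question:

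- the GEE of Asthma Impact at visits 3, 4 and 5 on class, for whether classes differ in later quality of life (Aim 2);
- the same GEE with the visit-1 Asthma Impact T-score added, for whether class predicts later quality of life beyond the starting score.

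Report them side by side, and base any claim of prediction beyond baseline only on the second.

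The cost is one covariate already collected and one extra model. There are three drawbacks. The adjusted class difference will be smaller. Measurement error in the visit-1 score leaves some carry-over, so a modest adjusted effect still needs caution. And adjustment does not cure the separate overlap that arises because the LTA uses data from visits 3-5, the outcome visits. Stating whether Asthma Impact is among the LTA indicators would let readers judge that overlap.

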### **Plan for supplemental R01 funding (aims 4-5)**

Aim 4 will determine associations between neighborhood air quality indices (predictor variables) and patient-reported asthma control and symptoms, lung function, exacerbation rates and QOL (outcome variables) during two separate seasons (spring/summer versus fall/winter) in children stratified by high- versus low-to-moderate social vulnerability. Prespecified outcomes are continuous and will be evaluated with linear regression. Analyses will be stratified by social

vulnerability (high versus low-to-intermediate) and season (spring/summer versus fall/winter). Models will be generated for air quality variables on the visit date and for each of the five lag days prior to the visit. Given the relatively small number of participants and high number of air quality predictor variables, we will use ElasticNet to select the most important variables in Python. Variables with a Pearson correlation coefficient  $>0.8$  will be removed to minimize redundancy. Models will be evaluated considering pertinent covariates such as age, asthma medications and tobacco smoke exposure. To further address sex as a biological variable, models will also be fitted by sex, with statistical comparison of results observed in boys and girls. Analyses will assume a type 1 error rate of 0.05 without adjustments for multiple testing (exploratory study). For exploratory dichotomized outcomes that are not pre-specified, such as exacerbation occurrence or QOL scores below a threshold, partial least squares regression and discriminant analysis could be performed to determine the air quality features that provide the largest separation between outcomes. Temporal stability of the results would be assessed by repeating analyses during the second season.

Aim 5 will determine whether children with greatest social vulnerability and the highest air pollution exposure will have differentially expressed cytokines and metabolomic features. Cytokine and metabolomics data will be integrated using the R package Multiple Co-inertia (MCIA) to identify novel biomarkers of climate-related outcomes. These co-inertial analyses (CIA) are similar to the sparse Partial Least Squares (sPLS) approach used to integrate multi-omics data in the analyses pipeline from the popular package mixOmics by maximizing the covariance between eigenvectors and efficiently determining key features driving variance in paired multi-omics samples. Unlike sPLS, CIA allows us to project multi-omic data in the same space, reducing the need to generate several paired multi-omic integration modules.

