Through supplemental funding, the study team will also test the central hypothesis that climate change-induced disruptions in air quality worsen asthma inflammation, symptoms, and longitudinal outcomes in school-age children with asthma and that these effects are mediated by social vulnerability. Two additional aims to be pursued are below:

**Aim 4. Determine associations between climate, air quality, symptoms, and outcomes in children with exacerbation-prone asthma during two climate seasons.**

Hypothesis: Children with greatest social vulnerability will have more air pollution exposure, increased symptoms, poorer lung function, more exacerbations and decreased QOL during each season.

**Aim 5. Determine the biological impact of climate and pollutants in children with exacerbation prone asthma.** Children with greatest social vulnerability and the highest air pollution exposure will have differentially expressed cytokines and metabolomic features.

This project involves a multidisciplinary team with a history of collaboration and is aligned with the NINR Strategic Plan to “*Advance Symptom Science Research*” in chronic conditions through biobehavioral research. The study population, children with exacerbation-prone asthma, has also been understudied in this regard. This project is expected to: 1) refine knowledge regarding the identification and clinical utility of symptom clusters in these children, and 2) identify mechanisms underlying symptom clusters that can be targeted in future interventional studies, to reduce the high morbidity and improve quality of life.

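### Aim 4 hypothesises differences between social-vulnerability groups, but its plan fits only separate within-group models, so that hypothesis is left untested

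*Combined protocol and SAP*

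**What the plan says.** Section B, under the supplemental aims, states the Aim 4 hypothesis as a contrast between groups: "Children with greatest social vulnerability will have more air pollution exposure, increased symptoms, poorer lung function, more exacerbations and decreased QOL during each season". The central hypothesis just above it adds, of the effects of disrupted air quality on asthma, that "these effects are mediated by social vulnerability".

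Section U, in the plan for aims 4-5, assigns the roles differently. It opens: "Aim 4 will determine associations between neighborhood air quality indices (predictor variables"; asthma control and symptoms, lung function, exacerbation rates and quality of life are the outcomes. These associations are to be estimated "in children stratified by high- versus low-to-moderate social vulnerability". The method is given as "Prespecified outcomes are continuous and will be evaluated with linear regression". Fitting is split by "vulnerability (high versus low-to-intermediate) and season (spring/summer versus fall/winter". The adjustment variables are "pertinent covariates such as age, asthma medications and tobacco smoke exposure", a list that does not name vulnerability. For sex, the same section goes a step further: "models will also be fitted by sex, with statistical comparison of results observed in boys and girls". No such step is written for vulnerability. Testing is at 0.05 without multiplicity adjustment, and the work is labelled exploratory.

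**The concern.** The hypothesis is about how two groups of children differ. A regression fitted inside one group holds group membership constant, so it cannot estimate the effect of membership. Followed exactly, the plan would produce pollutant slopes for high-vulnerability children and others for the remaining children, with no estimate, interval or test for the differences the hypothesis predicts.

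Two things are at stake. Part of the hypothesis, the higher exposure, would receive no analysis at all. And with no planned contrast, a reader of the results may fall back on noting that a pollutant was significant in one group and not in the other, which is not evidence that the groups differ.

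**Working it through.** **1. Hypothesis against planned analysis.**

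| Element in Section B | What Section U provides |
|---|---|
| More exposure in vulnerable children | Air quality is only a predictor; never compared between groups |
| Worse symptoms, lung function, exacerbations, quality of life | Each outcome modelled within groups; no difference in level estimated |
| Holds in each season | Models split by season, but no group contrast within a season |
| Effects mediated by vulnerability | No mediator model, no interaction term |

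Other parts of Section U do not fill the gap. The optional partial least squares and discriminant analysis separates outcome groups by air quality features, not vulnerability groups. The second-season repeat addresses temporal stability. The Aim 5 plan integrates cytokine and metabolomic data.

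**2. Why the fitted models leave the contrasts out.** Write the model in group g (H = high, L = lower) as E(Y) = a_g + b_g·X, with X an air quality index. The hypothesis and its background claim involve three contrasts:

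- exposure: mean X in H minus mean X in L;
- outcome level: (a_H + b_H·mean X in H) − (a_L + b_L·mean X in L);
- slope: b_H − b_L.

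Section U estimates a_g and b_g separately and stops there. The second contrast also shows that a vulnerability coefficient from a model containing X is not the hypothesised difference in level: it is the difference at one fixed X and removes the part that arises because vulnerable children are more exposed.

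**3. The only power figure in the documents.** Section T, Table 3, gives 0.808 for N = 147, 3 degrees of freedom and W = 0.275. Check: non-centrality = 147 × 0.275² = 11.12; critical chi-square at 0.05 = 7.815; power = 0.8084. The figure reproduces, but it belongs to the parent study's chi-square test. Nothing equivalent is given for Aim 4.

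**4. Illustration of reading significance group by group.** Suppose the true slope is the same in both groups. With power p₁ and p₂, exactly one group is significant with probability p₁(1 − p₂) + p₂(1 − p₁), which is 2p(1 − p) when the powers are equal:

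- p = 0.50: 2 × 0.50 × 0.50 = 0.50
- p = 0.65: 2 × 0.65 × 0.35 = 0.455
- p = 0.80: 2 × 0.80 × 0.20 = 0.32

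Letting power follow group size, take N = 147 (assumed to apply to Aim 4), a two-sided 0.05 test, standardised slopes of 0.2 to 0.3, splits from 50:50 to 25:75, and p ≈ Φ(slope × √n − 1.96). The lowest result is the 50:50 split with slope 0.3: p = 0.730 in each group, giving 2 × 0.730 × 0.270 = 0.39. The highest is 25:75 with slope 0.25: p = 0.329 and 0.747, giving 0.329 × 0.253 + 0.747 × 0.671 = 0.58.

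**5. Precision once the contrasts are added**, under the same assumed N and splits. With s = √(1/n_H + 1/n_L), the standardised difference detectable with 80% power is (1.96 + 0.84) × s. Interaction power for a slope of 0.3 in one group and 0 in the other is Φ(0.3/s − 1.96).

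| Split | s | Detectable difference | Interaction power |
|---|---|---|---|
| 50:50 | 0.165 | 0.46 | 44% |
| 33:67 | 0.175 | 0.49 | 40% |
| 25:75 | 0.190 | 0.53 | 35% |

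These figures count 147 children once each; fewer children in a given season would make season-specific contrasts less precise.

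**The case against.** The strongest reply is that the aim, as titled, is to determine associations between climate, air quality, symptoms and outcomes, and that the stratified regressions do this. That stands. A reader might infer that Aim 4 cannot answer its own question; the documents do not support so broad a claim. What goes untested is the hypothesis beneath the aim.

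A second reply is that the work is exploratory. Section U uses that label to justify leaving multiplicity unadjusted. It limits the harm, but it does not supply a contrast that the hypothesis needs.

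Third, nothing in Section U says the groups will be compared by which one crosses 0.05. That is also right. Such a reading is a foreseeable use of the output, not a planned step, so the percentages above measure a risk and not an error in the plan. They also treat each group as having one test, whereas the plan selects among many pollutants by ElasticNet and considers the visit date and five lag days.

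Fourth, a slope difference could be computed afterwards from two separate fits. It could, if the same pollutant is retained in both groups; selection within groups may not ensure that. It would still leave exposure and outcome level uncompared. That the authors wrote a comparison step for sex and none for vulnerability makes it hard to treat one as implied.

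Finally, one might read the central hypothesis as saying that vulnerability changes the pollutant effect. The text says mediated, which is a different claim. Neither reading has an analysis.

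**Conclusion.** The point holds for the Aim 4 hypothesis. Section B predicts differences between vulnerability groups in exposure and outcomes in each season, and Section U plans no model that estimates a vulnerability difference in exposure, outcome level or slope, and no mediation analysis. This follows from the text and rests on no numerical assumption.

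It does not follow that the stratified models are useless, that the whole aim fails, or that the parent study's primary and secondary analyses are affected. The figures for one group being significant and the other not (32% to 50% at assumed equal power of 80% to 50%; 39% to 58% over the assumed slopes and splits) are illustrative only. The documents state no Aim 4 power, effect size, sample size or vulnerability split. For a supplemental, exploratory aim this is a change that should be made before analysis.

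**What to change.** 1. Define the vulnerability measure and its cut-point, and use one name for the lower group, which Section U calls both low-to-moderate and low-to-intermediate.
2. For each air quality index as an outcome, and for each clinical outcome without pollutant adjustment, estimate the high-minus-lower vulnerability difference with a 95% confidence interval in each season. Use the covariates already named where appropriate.
3. Select pollutants and lags in the pooled sample. For those selected, fit one pooled model with vulnerability, season, pollutant and the vulnerability-by-pollutant interaction. Report the group slopes and the interaction, with its confidence interval, from that model.
4. Where a child contributes to both seasons, use generalized estimating equations or a mixed model. Option 2 visits run from week 0 to week 48, so this can be expected.
5. Either replace mediated by modified in the central hypothesis, or specify a mediation model with its exposure, mediator, outcome and assumptions.

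The cost is revised wording and a few extra models on data the aim already uses, with no added visits or recruitment. The interaction will be estimated imprecisely (power of about 35% to 44% in the illustration), so it should be reported as an estimate with its interval and not judged by its p-value alone.
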